### **Breadth Coverage**

Another breadth panel summary will be based on the phylogenetic distance based weighting method. The algorithm weighs the fraction of ELISA antigens that reach a given concentration with a distance factor, favoring ELISA antigen pairs with greater sequence distances, and therefore show broader coverage

Using the *Neighbor Joining method* and *Jukes-Cantor distance measure* and constructed in CLC Main Workbench 23.0.5 (QIAGEN Aarhus, Denmark), HA amino acid sequence alignment and

the phylogenetic tree will be generated. For each pair of IgG binding ELISAs as identified in **Table 5**, the phylogenetic distance factor was calculated (**Table 6**).

**Table 6: Phylogenetic distance matrix**

HA	Strain	H1_Cal	H1_Vic	H1_SC	H1_NC	H2_2005	H2_2020	H5_cam	H5_Vnm	H11	H17	H9_HK	H9_Camb
H1	A/California/07/2009 (UFV181009)	0	0.05	0.15	0.24	0.45	0.43	0.49	0.47	0.63	0.71	0.74	0.73
H1	A/Victoria/2570/2019 (UFV221619)	0.05	0	0.18	0.25	0.45	0.43	0.5	0.47	0.62	0.69	0.72	0.71
H1	A/South Carolina/1/1918 (UFV181084)	0.15	0.18	0	0.16	0.39	0.37	0.46	0.43	0.61	0.67	0.64	0.69
H1	A/New Caledonia/20/1999 (UFV181089)	0.24	0.25	0.16	0	0.45	0.42	0.47	0.47	0.64	0.7	0.68	0.7
H2	A/Env/MPU3156/2005 (UFV181154)	0.45	0.45	0.39	0.45	0	0.03	0.3	0.28	0.62	0.65	0.66	0.7
H2*	A/avian/Japan/KU-d3c/2020 (UFV235127)	0.43	0.43	0.37	0.42	0.03	0	0.29	0.27	0.59	0.63	0.65	0.68
H5*	A/Cambodia/NPH230032/2023 (UFV235130)	0.49	0.5	0.46	0.47	0.3	0.29	0	0.1	0.61	0.69	0.73	0.78
H5	A/Vietnam/1203/2004 (UFV190837)	0.47	0.47	0.43	0.47	0.28	0.27	0.1	0	0.59	0.68	0.7	0.77
H11	A/Env/MPK655/2009 (UFV190050)	0.63	0.62	0.61	0.64	0.62	0.59	0.61	0.59	0	0.79	0.69	0.69
H17	A/bat/Guatemala/060/2010-(UFV190401)	0.71	0.69	0.67	0.7	0.65	0.63	0.69	0.68	0.79	0	0.79	0.77
H9	A/Hong Kong/1073/1999 (UFV181156)	0.74	0.72	0.64	0.68	0.66	0.65	0.73	0.7	0.69	0.79	0	0.15
H9*	A/Cambodia/21020301/2021 (UFV235131)	0.73	0.71	0.69	0.7	0.7	0.68	0.78	0.77	0.69	0.77	0.15	0

The Breadth coverage area under the curve (AUC) will be calculated for each participant only when all ELISAs used in the calculation are non-missing. For each ELISA included in the breadth coverage calculation, values below LLOQ will be imputed with the LLOQ, and values above the upper limit of quantification (ULOQ) will be imputed with the ULOQ. All ELISA values will be normalized to  $\log_{10}$  [original value / LLOQ value] prior to calculation of the Breadth coverage.

Breadth coverage plots will be generated based on all relevant IgG binding ELISAs and their distance factors for each subject. To quantify the coverage of breadth of binding ELISAs, the area under the curve (AUC) will be calculated by using the trapezoidal rule. Breadth coverage plots and AUC calculations will be generated and performed using R package “tidyverse” and “ggprism”.

For the Breadth coverage AUC, the following results will be calculated: N, mean and corresponding 95% CI, interquartile range, min, max of the actual values, and mean increases from baseline will be tabulated and graphically presented. Reverse cumulative breadth coverage plots for each group will be presented based on individual breadth coverage. Least square means between active groups and the placebo group (pooled across cohort 1 and 2), with corresponding 95% CIs will be estimated via an analysis of variance (ANOVA), using post-baseline value as a dependent variable and study group as independent variable. As a sensitivity analysis, the ANOVA may also be performed adjusting for the respective baseline value, by including baseline value as an additional covariate.

## **Extended Breadth Coverage**

Same as for extended breadth scores, Extended Breadth Coverage was calculated using additional extended breadth panel. Results are presented in a similar way as described above for the Breadth coverage.

**Nasal antibody response** may be assessed using IgA and/or IgG ELISA in nasal secretions and presented in a similar way as described above for the core ELISAs and VNA. Nasal antibody response will be done on the same subject selection as for extended breadth ELISA panel for the FLZ1001 study only at Day 1 and Day 29. Two different types of nasal swab are used in the study, namely nylon flock and SAM. Attempt to normalize values reported by two different swab types will be made to be able to pool results in same summary table. If normalization will not be successful, the data will instead be summarized by swab type.

### **5.7.1.6. External control group from VAC31518COV3005 study**

VAC31518COV3005 (COV3005) is a randomized, double-blind, phase 3 study to evaluate safety, reactogenicity, and immunogenicity of co-administration of Ad26.COV2.S and influenza vaccines in healthy adults 18 years of age and older. The study aims to assess the safety, reactogenicity, and immunogenicity of the Ad26.COV2.S vaccine co-administered with a quadrivalent standard-dose or high-dose seasonal influenza vaccine compared to administration of each vaccine separately to explore whether Ad26.COV2.S and the influenza vaccines can be administered concomitantly.

Without a seasonal flu vaccinated control group in FLZ1001, samples from COV3005 participants will be used to assess the performance of FLZ1001 assays and stem binding response upon seasonal influenza vaccination. Samples from COV3005 participants will be used as an external control group and referred to as a Seasonal Flu vaccinated reference Serum Collection (“SF-SC”). Those samples will run alongside FLZ1001 study samples in all assays. The COV3005 study includes the same target population as the FLZ1001 study, healthy adults aged  $\geq 18$  to  $\leq 45$  years, and also includes older adults, the main envisioned target population of the Uniflu vaccine.

Details on the purpose and random selection of samples are presented in Universal Influenza Vaccine Study plan in COV3005 (TV-REF-281637).

#### **5.7.1.6.1. Populations (analysis sets) for COV3005 analysis**

**Broad SF-SC:** At the first stage, 200 subjects who received the standard dose seasonal flu vaccination and did not receive Ad26.COV2.S vaccination (Broad SF-SC) were randomly selected to assess the performance of FLZ1001 assays on seasonal flu-vaccinated subjects (stratified by age group).

**SF-SC:** At the second stage, out of those 200 subjects a subset (SF-SC) will be selected to match as much as possible the population enrolled in FLZ1001. A direct comparison of FLZ1001 immunogenicity data will be made to the SF-SC cohort.

### 5.7.1.6.2. Humoral assays

Descriptive statistics and graphs on humoral immunogenicity data listed in [Table 4](#) (where available) will be done similarly as described in section [5.7.1.5.1.](#) for the COV3005 Broad SF-SC cohort (H5 ELISA, mini-HA ELISA, VNA, Human Fc $\gamma$ RIIIa reporter assay, breadth ELISAs including three breadth scores, coverage score, and HAI assay) and for the SF-SC cohort.

For H5 ELISA, mini-HA ELISA, VNA, Human Fc $\gamma$ RIIIa reporter assay, and three breadth scores, geometric mean ratios (GMR)  $\ddagger$  between active groups (FLZ1001 vs. SF-SC cohort), with corresponding 95% CIs will be estimated via an analysis of variance (ANOVA), using log-transformed 28 days post-dose 1 immune parameter response as dependent variable and study group as independent variable. As a sensitivity analysis, the ANOVA may also be performed adjusting for the respective baseline titers, by including log-transformed baseline titer as an additional covariate.  $\ddagger$ by back-transform LSmean and corresponding 95%CI from ANOVA [i.e.,  $10^{LSmean}$ ] and CI [i.e.,  $10^{CI}$ ].

In addition, GMR plots over time, combining the regimens in one graph (without individual participant dots) will also be created.

For the breadth coverage, least square mean differences between active groups (FLZ1001 vs. SF-SC cohort), with corresponding 95% CIs will be estimated via an analysis of variance (ANOVA), using 28 days post-dose 1 breadth coverage as dependent variable and study group as independent variable. As a sensitivity analysis, the ANOVA may also be performed adjusting for the respective baseline value, by including baseline breadth coverage as an additional covariate.

#### HAI assays (for each of the 4 influenza vaccine strains from COV3005 study).

For HAI assays data following results will be calculated for each of 4 influenza vaccine strains used in the study: N, geometric mean $\ddagger$  and corresponding 95% CI of the actual values and fold increases from baseline will be tabulated and graphically presented.  $\ddagger$ calculate the mean and corresponding 95% CI of log2transformed values, back-transform this mean [i.e.,  $2^{mean}$ ] and CI [i.e.,  $2^{CI}$ ].

- Seroconversion is defined for each of the influenza vaccine strains at 28 days after the administration of a seasonal influenza vaccine:
  - HI titer  $\geq 1:40$  in participants with a pre-vaccination HI titer of  $< 1:10$ , or
  - a  $\geq 4$ -fold HI titer increase in participants with a pre-vaccination HI titer of  $\geq 1:10$
- Seroprotection is defined for each of the influenza vaccine strains as HI titer  $\geq 1:40$ .

Tables will show the seroprotection, seroconversion, and fold increases.

Actual values and fold changes from baseline are tabulated and shown as dot plots with dots for participant values, and the corresponding geometric mean and 95% CI per time point for each assay.

In the graphs, original values will be displayed on the log2 scale. The actual values will be shown, even if they are below the LLOQ. The LLOQ cut-off will be visualized in the graph per assay.

A scatterplot with the age, mini-HA ELISA, and H5-ELISA versus HAI titers (per each 4 influenza vaccine strains), will be provided for the most important time points (at minimum, baseline, Day 29, and fold increase from baseline at Day 29).

A scatterplot with the HAI titers fold increase from baseline at Day 29 vs. baseline HAI titers will be provided.

### **5.7.2. Definition of Subgroups**

- For FLZ1001 and the SF-SC cohort of COV3005, demographic data and immunogenicity data (selected tables and graphs on H5-ELISA, mini-HA ELISA, VNA, Human Fc $\gamma$ RIIIa reporter assay, and Breadth of the antibody response) will be presented also by sex.
- For the Broad SF-SC cohort of COV3005, demographic data and immunogenicity data (selected tables and graphs on H5-ELISA, mini-HA ELISA, VNA, Human Fc $\gamma$ RIIIa reporter assay, Breadth of the antibody response, and HAI titers) will be presented also by
  - sex
  - age group
    - 18-45 years
    - 46-64 years
    - $\geq 65$  years
  - imprinting groups (according to the birth year):
    - <1957 H1N1
    - 1957-1967 H2N2
    - 1968-1976 H3N2
    - 1977-2009 H3N2 or H1N1

## **5.8. Interim Analyses**

There are no plans for interim analyses with an intent to stop the study early or to adapt the design or planned number of patients. However, there will be planned analyses at pre-specified timepoints as described in the study protocol (please refer to the CTP section 9.5 Planned Analyses).

DPS will identify which outputs will be produced for each analysis.

Based on safety and immunogenicity results, the sponsor's Vaccine Development Committee will decide which regimen will be taken forward. Additional factors such as data from other studies\* or other assays, literature, epidemiology data, manufacturability, and ease of administration will be considered to select the regimen for the next clinical study.

\*Additional analyses might be performed on immunogenicity data up to 29 days post-dose 1 from the external control group (COV3005 study). Two cohorts will be presented:

1. independent analysis will be performed on the Broad SF-SC cohort of COV3005 (200 subjects' cohort), followed by
2. selection of the SF-SC (matching ZLF1001 population) and analysis of the SF-SC cohort.

### **5.8.1. Data Monitoring Committee (DMC) or Other Review Board**

An internal Data Review Committee (DRC), consisting of members that are not directly involved in the study conduct, data management, or statistical analysis, will be established for this study,

and will monitor data to ensure the safety and well-being of the participants enrolled. For further details please refer to:

- CTP section 10.3. Appendix 3: Regulatory, Ethical, and Study Oversight Considerations, **Data Review Committee** section.
- DRC charter (EDMS-ERI-199974976)
- DRC SAP (EDMS-ERI-206674654)

## 6. SUPPORTING DOCUMENTATION

### 6.1. Appendix 1 List of Abbreviations

ADaM	Analysis Data Model
AE	adverse event
ATC	anatomic and therapeutic class
BMI	body mass index
CI	confidence interval
CRF	case report form
CTP	clinical trial protocol
DMC	Data Monitoring Committee
DPS	data presentation specifications
DRC	Data Review Committee
ELISA	enzyme-linked immunosorbent assay
FAS	full analysis set
FDA	Food and Drug Administration
Flu-iiQ™	Influenza Intensity and Impact Questionnaire
GMC	Geometric Mean Concentration
GMR	Geometric Mean Ratio
GMT	Geometric Mean Titre
HAI	hemagglutination inhibition
ILI	Influenza-like illness
LLOQ	lower limit of quantification
LOD	Limit of detection
mini-HA	hemagglutinin stem-derived protein vaccine antigen
MedDRA	Medical Dictionary for Regulatory Activities
NA	not applicable
RT-PCR	reverse transcriptase polymerase chain reaction
PPI	per protocol immunogenicity analysis set
SAE	serious adverse event
SAP	Statistical Analysis Plan
SD	standard deviation
SDTM	Study Data Tabulation Model
SF-SC	Seasonal Flu Vaccinated Reference Serum Collection
SMQ	standardized MedDRA query
ULOQ	upper limit of quantification
VNA	virus neutralizing antibody
WHO	World Health Organization

**6.2. Appendix 2 Changes to Protocol-Planned Analyses**

None to describe at the drafting of SAP version 1.0.

### 6.3. Appendix 3 Demographics and Baseline Characteristics

The following demographic and baseline characteristics will be summarized.

[Table 7](#) presents a list of the demographic variables that will be summarized by vaccine regimen and overall for the FAS.

**Table 7: Demographic Variables**

Continuous Variables:	Summary Type
Age (years)	Descriptive statistics (N, mean, standard deviation [SD], median, and range [minimum and maximum]).
Weight (kg)	
Height (cm)	
Body Mass Index (BMI) (kg/m  )	
Categorical Variables	
Sex (male, female, undifferentiated, unknown)	Frequency distribution with the number and percentage of participants in each category.
Race a (American Indian or Alaska Native, Asian, Black or African American, Native Hawaiian or other Pacific Islander, White, Not reported, Unknown)	
Ethnicity (Hispanic or Latino, not Hispanic or Latino)	

aIf multiple race categories are indicated, the Race is recorded as 'Multiple'

#### **6.4. Appendix 4 Protocol Deviations**

Major protocol deviations will be summarized.

In general, the following list of major protocol deviations may have the potential to impact participants' rights, safety or well-being, or the integrity and/or result of the clinical study. Participants with major protocol deviations will be identified prior to database lock and the participants with major protocol deviations will be summarized by category.

- Developed withdrawal criteria but not withdrawn
- Entered but did not satisfy criteria
- Received a disallowed concomitant treatment
- Received wrong vaccination regimen or incorrect dose
- Other

Major protocol deviations which have a potential impact on immunogenicity will be flagged in the listings.

## 6.5. Appendix 5 Prior and Concomitant Medications

The analysis of concomitant therapies will be done using the WHO drug coded terms.

Based on their start and stop date, concomitant therapies will be reported in each applicable phase.

If a concomitant therapy record misses components of its start and/or stop dates (time, day and/or month and/or year):

- In case of partial start or stop dates, the concomitant therapy records will be allocated to periods using the available partial information, without imputations. If, for example, only month and year are available, these will be compared to the month and the year of the periods, and the concomitant therapy record will be allocated to the period(s) where these date parts match. This rule may lead to assignment to multiple periods.
- In case of a completely missing end date, the concomitant therapy will be considered as ongoing at the end of the trial.

There will be special attention to any systemic use of analgesics/antipyretics, started during [8] days following each vaccination (00:00 of day of vaccination + [7] days). Following ATC/DD codes will be used for this: N02A (OPIOIDS) and N02B (OTHER ANALGESICS AND ANTIPYRETICS), M01A (ANTIINFLAMMATORY AND ANTIRHEUMATIC PRODUCTS, NON-STEROIDS) and M01B (ANTIINFLAMMATORY/ANTIRHEUMATIC AGENTS IN COMBINATION) (ATC/DD Index). The classes will be added in a footnote in all related tables and listings. For the use of analgesics/antipyretics which are taken on the day of vaccination, an exception is made in case the time is before vaccination. In this case, the concomitant medication is also allocated to the post-dose period.

## 6.6. Appendix 6 Guidance for Industry: Toxicity Grading Scale for Healthy Adult and Adolescent Volunteers Enrolled in Preventive Vaccine Clinical Trials

Refer to the Appendix 5 of the CTP for Toxicity Grading Scale.

The laboratory values provided in Appendix 5 of the CTP serve as guidelines and are dependent upon institutional normal parameters. Institutional normal reference ranges should be provided to demonstrate that they are appropriate.

If a laboratory value falls within the grading as specified below but also within the local laboratory normal limits, the value is considered to be normal and will be reset to grade 0.

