* The laboratory values provided in the tables serve as guidelines and are dependent upon institutional normal parameters. Institutional normal reference ranges should be provided to demonstrate that they are appropriate.

** The clinical signs or symptoms associated with laboratory abnormalities might result in characterization of the laboratory abnormalities as potentially life-threatening (Grade 4). For example, a low sodium value that falls within a Grade 3 parameter (125-129 mEq/L) should be recorded as a Grade 4 hyponatremia event if the participant had a new seizure associated with the low sodium value.

*** ULN is the upper limit of the normal range.

Hematology *	Mild (Grade 1)	Moderate (Grade 2)	Severe (Grade 3)	Potentially Life Threatening (Grade 4)
Hemoglobin (Female) - gm/dL	11.0 - 12.0	9.5 - 10.9	8.0 - 9.4	< 8.0
Hemoglobin (Female) change from baseline value - gm/dL	Any decrease - 1.5	1.6 - 2.0	2.1 - 5.0	> 5.0
Hemoglobin (Male) - gm/dL	12.5 - 13.5	10.5 - 12.4	8.5 - 10.4	< 8.5
Hemoglobin (Male) change from baseline value - gm/dL	Any decrease - 1.5	1.6 - 2.0	2.1 - 5.0	> 5.0
WBC Increase - cell/mm3	10,800 - 15,000	15,001 - 20,000	20,001 - 25,000	> 25,000
WBC Decrease - cell/mm3	2,500 - 3,500	1,500 - 2,499	1,000 - 1,499	< 1,000
Lymphocytes Decrease - cell/mm3	750 - 1,000	500 - 749	250 - 499	< 250
Neutrophils Decrease - cell/mm3	1,500 - 2,000	1,000 - 1,499	500 - 999	< 500
Eosinophils - cell/mm3	650 - 1500	1501 - 5000	> 5000	Hypereosinophilic
Platelets Decreased - cell/mm3	125,000 - 140,000	100,000 - 124,000	25,000 - 99,000	< 25,000
PT - increase by factor (prothrombin time)	1.0 - 1.10 x ULN**	1.11 - 1.20 x ULN	1.21 - 1.25 x ULN	> 1.25 ULN
PTT - increase by factor (partial thromboplastin time)	1.0 - 1.2 x ULN	1.21 - 1.4 x ULN	1.41 - 1.5 x ULN	> 1.5 x ULN
Fibrinogen increase - mg/dL	400 - 500	501 - 600	> 600	--
Fibrinogen decrease - mg/dL	150 - 200	125 - 149	100 - 124	< 100 or associated with gross bleeding or disseminated intravascular coagulation (DIC)

* The laboratory values provided in the tables serve as guidelines and are dependent upon institutional normal parameters. Institutional normal reference ranges should be provided to demonstrate that they are appropriate.

** ULN is the upper limit of the normal range.

Urine *	Mild (Grade 1)	Moderate (Grade 2)	Severe (Grade 3)	Potentially Life-Threatening (Grade 4)
Protein	Trace	1+	2+	Hospitalization or dialysis
Glucose	Trace	1+	2+	Hospitalization for hyperglycemia

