### **5.6.2.      Laboratory, Vital Signs, and Physical Examination**

For laboratory safety parameters and vital signs, only abnormalities emerging after vaccination will be tabulated by worst abnormality grade using the FDA table in Protocol Appendix 5.

Vital signs including temperature, pulse/heart rate, respiratory rate, and blood pressure (systolic and diastolic) will be summarized over time, using descriptive statistics. Abnormalities emerging after vaccination will be tabulated by worst abnormality grade using the FDA table in Protocol Appendix 5.

An abnormality (toxicity grade or abnormality based on normal ranges) will be considered as emerging in a particular period if it is worse than the baseline value. If the baseline is missing, the abnormality is always considered emerging. A shift from ‘abnormally low’ at baseline to ‘abnormally high’ post baseline (or vice versa) is also emerging. In case a laboratory test result is censored (no numeric value is available, but only a verbatim term) then a numeric value will be imputed by a value exceeding the cut-off value with one unit. (<x: subtract 1 unit from x, >x: add 1 unit to x; eg <3.45 is imputed with 3.44).

In case no toxicity grades are defined for a test, the abnormalities (above/below normal range) will be used. In determining toxicity grades, the following rules are applied:

- Worst grades/abnormalities are determined over the whole observational period for each trial period separately, including all post-baseline measurements of that period.
- The abnormalities ‘abnormally low’ and ‘abnormally high’ are considered equally important, i.e., if a participant has an abnormally low as well as an abnormally high value post-baseline, both abnormalities are shown in the tables. (This means that the sum of the percentages can be more than 100%)
- Note: as the grading scale for some parameters in the grading table has some gaps (zones where no toxicity grade definition exists), laboratory results falling in these zones will be allocated to the adjacent worst-case grade.
- If a lab value falls within the grading as specified in the grading table but also within the local lab normal limits, the value is considered as normal.

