### Ranges to convert FDA scale to SI units

Ranges to convert FDA scale to SI units		Mild (Grade 1)	Moderate (Grade 2)	Severe (Grade 3)	Potentially Life Threatening (Grade 4)
Albumin (g/L)	Hypo-albuminemia	28 - 31	25 - 27	< 25	
Eosinophils (10  /L)		0.65 - 1.5	1.501 - 5.0	> 5.0	
Hemoglobin for male (g/L)		125 - 135	105 - 124	85 - 104	< 85
Hemoglobin for female (g/L)		110 - 120	95 - 109	80 - 94	< 80
Hemoglobin change from baseline (g/L)		Any decrease – 15	16 - 20	21 - 50	> 50
Lymphocytes (10  /L)		0.75 - 1.0	0.5 - 0.749	0.25 - 0.499	< 0.25
Neutrophils (10  /L)		1.5 – 2.0	1.0 – 1.499	0.5 – 0.999	< 0.5
Platelets (10  /L)		125 – 140	100 – 124	25 – 99	< 25
Protein (g/L)	Hypo-proteinemia	55 – 60	50 – 54	< 50	
WBC (10  /L)	Increase	10.8 – 15	15.001 – 20	20.001 – 25	> 25
	Decrease	2.5 – 3.5	1.5 – 2.499	1.0 – 1.499	< 1.0

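### As worded, the SAP's reset of in-range laboratory values to Grade 0 also removes haemoglobin change-from-baseline grades for falls that end within local normal limits

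*SAP*

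**What the plan says.** SAP 5.6.2 defines the laboratory output: "For laboratory safety parameters and vital signs, only abnormalities emerging after vaccination will be tabulated by worst abnormality grade", using the grading table in protocol Appendix 5. Summary statistics over time are specified there for vital signs only.

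The reset appears twice. In 5.6.2 the condition is: "If a lab value falls within the grading as specified in the grading table but also within the local lab normal limits". The value then counts as normal. In Appendix 6 (6.6) the condition is: "If a laboratory value falls within the grading as specified below but also within the local laboratory normal limits". The consequence is that "the value is considered to be normal and will be reset to grade 0".

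The SI-unit table that follows in Appendix 6 holds absolute haemoglobin rows for men and women and also a change row ("Hemoglobin change from baseline (g/L"). Protocol Appendix 5 has the same change row by sex, for example "Hemoglobin (Female) change from baseline value - gm/dL". Neither SAP section exempts the change row from the reset, and neither says how the absolute and change grades combine into a worst grade.

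**The concern.** The reset makes sense for a row graded on an absolute value. A fixed cut-off can overlap a laboratory's own normal range, and both documents describe the cut-offs as guidelines that depend on institutional norms. A change row does a different job: it flags a participant whose value has dropped a long way, whatever the level at which it ends. If the reset is applied to it, a large fall from a high-normal baseline to a low-normal value loses its grade.

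The worst-grade table is the only laboratory summary that 5.6.2 specifies. Haemoglobin is a protocol-required test, and haematology is scheduled after baseline on Days 8, 57 and 64. In a first-in-human study these tables exist to show individual graded events, so a rule that removes protocol-defined grades should at least be deliberate.

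**Working it through.** **Inputs from the documents**
- Change row, SAP Appendix 6: Grade 1 any decrease up to 15 g/L; Grade 2 16-20; Grade 3 21-50; Grade 4 above 50.
- Absolute rows, SAP Appendix 6: Grade 1 is 125-135 g/L in men and 110-120 g/L in women. Values above 135 or 120 g/L carry no absolute grade.
- Local normal limits are not given, so every limit below is an assumption.

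**Step 1: check the SAP's SI limits.** Protocol Appendix 5 has cut-offs of 1.5, 1.6, 2.0, 2.1 and 5.0 g/dL. Multiplied by 10 they give 15, 16, 20, 21 and 50 g/L, which is the SAP row exactly.

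**Step 2: apply the rule to falls that end within limits.**

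| Sex | Baseline to later value (g/L) | Fall | Change grade | Absolute grade | After reset as worded |
|---|---|---|---|---|---|
| Male | 165 to 147 | 18 | 2 | none | 0 |
| Male | 165 to 140 | 25 | 3 | none | 0 |
| Female | 150 to 132 | 18 | 2 | none | 0 |
| Female | 150 to 125 | 25 | 3 | none | 0 |

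Each result holds for any local range that contains the later value.

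**Step 3: which falls can be lost.** A Grade 2 fall can end in range if baseline is at least the lower limit + 16; a Grade 3 fall needs the lower limit + 21.
- Men, assumed limits 130-170, 136-175 or 140-180 g/L: baseline from 146, 152 or 156 (Grade 2) and from 151, 157 or 161 (Grade 3).
- Women, assumed limits 115-150, 121-155 or 125-160 g/L: from 131, 137 or 141 (Grade 2) and from 136, 142 or 146 (Grade 3).
- The largest fall that starts and ends in range equals the width of the range, here 34 to 40 g/L. That is Grade 3.

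**Step 4: expected numbers.** All assumed: men; baseline mean 153, SD 9 g/L; independent change mean -3, SD 7 g/L; values in whole g/L. The fall then has mean 3 and SD 7.
- P(Grade 2) = Φ((20.5 - 3)/7) - Φ((15.5 - 3)/7) = 0.9938 - 0.9629 = 0.031, or 150 × 0.031 ≈ 4.6 per 150.
- P(Grade 3) = Φ((50.5 - 3)/7) - Φ((20.5 - 3)/7) = 1.0000 - 0.9938 = 0.0062, or 150 × 0.0062 ≈ 0.93 per 150.

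The share of these falls that ends at or above the lower limit was simulated under the same assumptions:

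| Assumed lower limit (g/L) | Grade 2 share lost | Grade 2 lost per 150 | Grade 3 share lost | Grade 3 lost per 150 |
|---|---|---|---|---|
| 130 | 75% | 4.6 × 0.75 ≈ 3.5 | 53% | 0.93 × 0.53 ≈ 0.5 |
| 135 | 55% | 4.6 × 0.55 ≈ 2.5 | 32% | 0.93 × 0.32 ≈ 0.3 |
| 140 | 33% | 4.6 × 0.33 ≈ 1.5 | 16% | 0.93 × 0.16 ≈ 0.1 |

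The figure of 150 is the planned number of participants on active regimens, treated here as if all were men. The counts are per measurement.

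**The case against.** **The reset may not reach the change row at all.** The graded quantity in that row is a difference, and laboratories set normal limits for concentrations, not for a participant's own change. On that reading the two-part condition can never be met for the change row. This is a fair reading and may be the intended one. But the SAP does not state it, both versions of the rule speak of the laboratory value, and the Appendix 6 version points to the table that contains the row. Two programmers could implement it differently. The separate Data Presentation Specifications may settle the matter, but they are not among the documents reviewed, and the rule itself stands in the SAP.

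**A reader might infer that the change row would add nothing.** That is not so. The reset touches only values inside local limits. With an assumed lower limit of 135 g/L, a man falling from 165 to 130 g/L has absolute Grade 1 and change Grade 3 (a fall of 35). The value is out of range, so it is not reset and the change row raises his worst grade.

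**A reader might infer that such falls are hidden from safety oversight.** The documents do not support that. Under protocol 8.2.3 the investigator reviews laboratory results and records clinically relevant changes as adverse events. Protocol Appendix 5 has no reset, and the pausing rules in protocol 6.8 act on laboratory grades during conduct. SAP 5.1.1 provides listings by phase and time point.

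**The numbers are small and rest on assumptions.** This stands. The percentages in the working look large only because they are shares of rare events, so the counts are the better guide.

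**Conclusion.** The point holds as a wording defect with a limited effect. Applied as written, the reset removes Grade 2 and Grade 3 haemoglobin change grades from the SAP's worst-grade table when the fall ends within local normal limits; in-range Grade 1 falls go too. Grade 4 falls are not at risk under the ranges tried, because a fall above 50 g/L cannot fit inside a range 34 to 40 g/L wide.

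The size is about 1.5-3.5 Grade 2 and 0.1-0.5 Grade 3 falls per 150 participants per measurement. That depends on assumed baseline, change and lower-limit values for men, none of which the documents give. No primary endpoint, conduct rule or adverse event record is affected. It is a cheap improvement, not a flaw that threatens the study's conclusions.

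**What to change.** In SAP 5.6.2 and Appendix 6, state that the reset to Grade 0 applies only to rows graded on absolute values. Tabulate haemoglobin change from baseline as a separate row, with the protocol Appendix 5 grades, so that it is clear which row produced a grade.

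The cost is one sentence, stated in both places, and one table row. No data collection changes.

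The downside is that more graded haemoglobin abnormalities will be shown. At Grade 2 and above this is only a few. Most additions will be Grade 1, because that grade covers any decrease up to 15 g/L. Under the same assumptions P(Grade 1) = Φ((15.5 - 3)/7) - Φ((0.5 - 3)/7) = 0.963 - 0.360 ≈ 0.60 per measurement. A separate row keeps these small falls from being mixed with the absolute-value grades.
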